4.3 Excluded or Vulnerable Populations

- Although not the primary source of recruitment, eligible UIC students and employees are welcomed to participate with every effort taken to avoid any semblance of coercion (see section 5.0).
- Eligible volunteers from all racial or ethnic backgrounds are also welcomed to participate.
- Minors and pregnant women will be excluded by virtue of the scientific design. Moreover, the study question is not directed towards minors or pregnant women.

5.0 Subject Enrollment

Volunteers with PCOS will primarily be recruited from the principal investigator's (PI) Reproductive Endocrine referral practice located in the University of Illinois Hospital and Health System (UI Health) Outpatient Care Center (OCC), Suite 4A. The prevalence of PCOS in the general female population is ~15% but is as high as 80% in the referral based patient population cared for by the PI. Volunteers with PCOS will also be recruited through physician referral and from advertisements on UIC bulletin boards, electronic bulletin boards, websites such as Google.com, local newspapers and on social media. The advertisements will include a phone number and e-mail address to contact the PI or the Ob/Gyn Research Nurse Study Coordinator who will explain the study and administer a screening questionnaire using an approved eligibility checklist administered either over the phone, or via email correspondence using a secure UIC e-mail server containing a link to a confidential web-based screening questionnaire ([Screening Questionnaire – Treating Inflammation in Polycystic Ovary Syndrome to Ameliorate Ovarian Dysfunction](#)) through UIC's Qualitrics survey tool (<http://accc.uic.edu/service/surveys>). Advertisements, that correspond with IRB approved flyers or images, may be used on Facebook, Twitter, Instagram or the study website (<http://www.doyouhavepcos.org>). Prospective volunteers who view the images will be directed to contact the study phone or email address for more information. No direct contact with prospective volunteers will be made on these platforms. No data will be collected from these platforms. In addition, other care providers who become aware of the study may refer potential subjects for participation.

HealthMatch <https://healthmatch.io/> and CenterWatch <https://www.centerwatch.com/> are two online platforms that will also be used to assist with study recruitment. Prospective volunteers access these platforms to learn about clinical trials with open enrollment from publicly available information gathered by these platforms (e.g. study protocols descriptions listed on ClinicalTrials.gov). If a prospective volunteer expresses interest in study participation, the platform sends the investigator an email notification, but only provides the prospective volunteer's contact information at the investigator's request. The study team can subsequently use an appropriate IRB-approved recruitment tool to confirm interest in study participation and study eligibility such as email correspondence containing a link to our confidential web-based screening questionnaire as described above. No direct contact with prospective volunteers will be made on these platforms. No data will be collected from these platforms.

A targeted recruitment campaign will also be launched with the assistance of PCOS Challenge, the largest nonprofit support organization globally for women with PCOS serving over 45,000 members (2,542 in Illinois). PCOS Challenge membership grows at over 20% per year, and 92% of PCOS Challenge members have been diagnosed with PCOS. This will be a statewide recruitment campaign that includes: 1) One month of bi-weekly emails to members in Illinois sent by the PCOS Challenge Marketing and Public Relations Department; thus, the research team will not have direct access to any email addresses; 2) A study promotional page on the PCOS Challenge website (<http://www.pcoschallenge.org/>) with additional information about the study (i.e. title, description, goals, eligibility criteria, exclusions, etc.); 3) A 120mm x 240mm banner ad promoting the study on every page of PCOSChallenge.com (>40,000 pages). The email message to members, the promotional page PowerPoint presentation and the 120mm x 240mm banner ad are included for review.

The CCTS will further assist in identifying potential study participants using the CRDW–UIC CIRCLE as the data source. The data extracted through REDCAP will include age, height, weight, laboratory test results, diagnoses associated with PCOS, and contact information (see Data Request Authorization Form). The extracted data will subsequently be transferred to an Excel spreadsheet that will be stored by the PI in his password protected office computer under lock and key. A letter of introduction to the study will be sent to potentially eligible reproductive-age women whose data meet the profile for having PCOS, but only after obtaining permission from the UIC physicians who care for these women. The letter will indicate that the communication was sent with permission from their physician, and will contain study contact information to inquire about study participation or to request no further contact. The data from a given individual will initially be identified by medical record number (MRN), and then coded upon study enrollment when these individuals are assigned a study number. The link between an individual and the coded data will only be known to the PI. The coded data set without direct identifiers will be stored by the PI in his password protected office computer under lock and key. Only the PI and Co-investigators will have access to the coded data set.

Each volunteer will meet the PI (or his designee) in the UIC Center for Clinical and Translational Science's (CCTS) Clinical Research Center (CRC) to explain the scientific rationale, procedures and potential risks of the study, and the rights of the study participant. Informed consent will be obtained from each volunteer prior to participation in the study using a consent form approved by the UIC IRB. An electronic note will be written in each participant's medical record regarding the consent, and a copy of the consent form will be given to the participant. The original consent form will be kept with the investigator's study records.

Eligible volunteers will be informed that participation in the study is entirely voluntary, and that they may withdraw their consent at any time. They will also be assured that withdrawal from

the study will not affect their on-going care or their relationship with their physician in any way. Volunteers who fail the screening process will be promptly notified by telephone that they are not eligible to participate in the study. Data from screen failures will not be included in the study.

An honest and open recruitment process is employed to protect against the possibility of coercion or undue influence. Volunteers are encouraged at all stages to discuss their potential participation with trusted advisors including friends, family members, or medical personnel not connected with the study. The aim is to remain objective in the recruitment process to the point that volunteers have been excluded in the past on the basis of a perceived failure to reach a fully informed state regarding the study. There will not be any threat of harm or adverse consequences if the subject does not agree to participate in the study. For students or employees in particular, they will be reassured that their decision to participate or not to participate will not affect their grades (students) or standing in the University or Hospital. Furthermore, the information provided during the consent process will be presented in a balanced way with equal emphasis on all elements of consent (e.g. there will not be over-emphasis of benefits and under-emphasis of risks).

6.0 Study Design and Procedures

This research will involve the prospective study of 90 reproductive age women (18-40 years) with PCOS using a randomized double-blind placebo-controlled study design. The randomization schedule will be stratified by body mass index (BMI) (lean: BMI ≥ 18 but ≤ 25 kg/m²; obese: BMI ≥ 30 but ≤ 40 kg/m²) and IR status study groups to ensure a balance of patients in the two study arms. IR will be defined by the insulin area under the curve from 0-120 min (insulin AUC₀₋₁₂₀) of an oral glucose tolerance test (OGTT) $> 7,000$ which is highly predictive and thus, recommended for population assessment of IR in PCOS.³⁵ Forty five (45) of the women with PCOS will receive salsalate of which 30 will be lean (15 without IR; 15 with IR) and 15 will be obese. The other 45 women with PCOS with a similar frequency distribution of BMI and IR status will receive placebo. Thus, the study will be comprised of the following 6 groups:

1. Salsalate-treated lean PCOS without IR (n=15)
 - BMI ≤ 25 kg/m² – and – 2-hour oral glucose tolerance test (OGTT) insulin area under the curve (AUC) $\leq 7,000$
2. Placebo-treated lean PCOS without IR (n=15)
 - BMI ≤ 25 kg/m² – and – 2-hour OGTT insulin AUC $\leq 7,000$
3. Salsalate-treated lean PCOS with IR (n=15)
 - BMI ≤ 25 kg/m² – and – 2-hour OGTT insulin AUC $> 7,000$
4. Placebo-treated lean PCOS with IR (n=15)
 - BMI ≤ 25 kg/m² – and – 2-hour OGTT insulin AUC $> 7,000$
5. Salsalate-treated Obese PCOS – BMI ≥ 30 kg/m² – ≤ 40 kg/m² (n=15)
6. Placebo-treated Obese PCOS – BMI ≥ 30 kg/m² – ≤ 40 kg/m² (n=15)

After the initial pre-screening, volunteers will be asked to come to the CCTS CRC at [name] for a screening visit at ~ 8:00 AM. The screening visit will occur within 1 to 4 weeks of beginning the study protocol and will last ~4 hours. At the start of the screening visit, volunteers will undergo informed consent followed by a complete history and physical, vaginal sonography, and blood draws for a hormonal evaluation if not performed previously, a complete blood count (CBC), a comprehensive metabolic panel (CMP) and an OGTT. Based on the screening results, volunteers deemed eligible for study participation will subsequently enter the study protocol beginning between days 3 and 13 following the onset of either a spontaneous or progestin-induced withdrawal bleed, or without regard to the onset of menses if vaginal

sonography within 21 days of study start reveals no evidence of follicular development in the face of a negative pregnancy test.

Visits 1 through 5 will occur during the first week of the study protocol. During Visits 1 through 4, subjects will undergo an HCG stimulation test (HCG-ST) in the CRC consisting of a single IM HCG injection during Visit 1 after documenting a negative urine pregnancy test, along with a single blood draw during all 4 visits at 0, 24, 48 and 96 hours after HCG administration to measure serum androgens and 17-hydroxyprogesterone. Visits 1 through 3 will be short lasting ~30 minutes. After one of these short visits, subjects will also undergo a body composition assessment consisting of a whole-body dual-emission X-ray absorptiometry (DEXA) scan in the Integrative Physiology Laboratory (IPL) at [name], and a magnetic resonance image of the abdomen in the Center for Magnetic Resonance Research at [name]. Visit 4 will last ~8 hours during which a cream challenge test (CCT) will also be performed in the CRC consisting of dairy cream ingestion and serial blood draws at 0, 2, 3 and 5 hours after cream ingestion to measure inflammation markers. Visit 5 will last ~7 hours and occur 2 days after the CCT during which subjects will undergo a FS-IVGTT in the CRC to assess insulin sensitivity and glucose-stimulated inflammation.

[figure not shown]
| Table 1. PRE-STUDY SCREENING | | | | |
|--|---------|---|---|---|
| STUDY PROTOCOL | WEEKS → | 0 | 4 | 8 |
| Salicylate Level | | X | X | X |
| Sex Hormone Binding Globulin | | X | | X |
| Body Composition: MRI & DEXA | | X | | |
| HCG Stimulation Test: T, A & 17OHP @ 0, 24, 48 & 96 hours. | | X | | X |
| Cream Challenge Test: MNC-derived ROS, NFκB, RNA & protein inflammat'n markers @ 0, 2, 3 & 5 hours. | | X | | X |
| Frequently Sampled Intravenous Glucose Tolerance Test: glucose, insulin, C-peptide & FFA q 1-30 minutes x 34 samples from -20-240 minutes. | | X | | X |
| Post-Study Safety Tests: CBC & CMP. | | | | X |
| Ovulation Monitoring: BBT from 0-12 weeks; P on 7th day of BBT rise; If P >2 ng/dl documented, vaginal sonography on day of & day after LH surge. | | | | |

A predefined computer-generated randomization schedule set up by a statistician will have centralized allocation and codes secured by a research pharmacist. This schedule will be used to assign recruited subjects to receive salsalate (Amneal Pharmaceuticals, Bridgewater, NJ) 3 grams/day (lean subjects) or 4 grams/day (obese subjects) in 2 divided doses or identical placebo for ~12 weeks. Study medication will actually be administered over a range of 11 to 13 weeks to accommodate scheduling glitches without impacting any anticipated treatment effects. Subjects and study personnel will be blinded to the treatment assignment. Serum salicylate levels will be measured to assess compliance from a fasting blood sample drawn at baseline (Visit 1) and after 4 weeks (Visit 6), 8 weeks (Visit 7) and 12 weeks (Visit 8) of treatment. Compliance will be defined as salicylate levels being in the therapeutic range for rheumatology practice (10-30 mg/dl) during treatment. A Data and Safety Monitoring Board (DSMB) will keep track of salicylate levels to maintain blinding (see Section 6.0). A fasting lipid profile will also be drawn at baseline (Visit 1) and after 12 weeks (Visit 8) of treatment.

During treatment, all subjects will undergo ovulation monitoring consisting of serum progesterone measurements timed by basal body temperatures along with serial follicular ultrasonography as indicated. After the ~12 weeks of treatment, subjects will undergo repeat testing consisting of an HCG-ST during Visit 8 through 11, a CCT during Visit 11 and a FS-

IVGTT during Visit 12. Visits 8 through 12 will occur during the last week of the study protocol. See Table 1 for an overview of the study protocol and Fig. 2 for the study timeline.

Figure 2

Although it is anticipated that the majority of subjects will undergo the three main test procedures (i.e. HCG-ST, CCT and FS-IVGTT) in the order described, the order in which they will be scheduled may need to be changed to accommodate scheduling glitches, since they will be performed as outpatient procedures in accordance with the CCTS CRC operating hours. The change in order will not impact the integrity of the data.

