- **Ovulation Monitoring:** All subjects will maintain a basal body temperature (BBT) chart throughout the ~12 weeks of treatment after appropriate instructions. A blood sample (5 ml) will be drawn to measure serum progesterone to detect ovulation on the 7th day of temperature elevation of at least ¾°F from baseline indicative of a biphasic BBT response. Subjects will be instructed to alert the team regarding the potential need to schedule a progesterone measurement when 3 consecutive days of temperature elevation is evident. The length of the cycle in which a luteal range progesterone (>2 ng/ml) is documented will be used to time initiation of midcycle urine luteinizing hormone (LH) monitoring with a commercially available kit. Vaginal sonography will be performed in the CRC on the day of the color change signifying the LH surge and the following day to document follicular development and collapse, respectively, as the definitive evidence of ovulation.

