- *MNC Culture:* A blood sample will be drawn at 0 and 120 minutes of the CCT for MNC isolation. Whole blood will be diluted 1:2 with PBS (pH 7.4) and underlayered with histopaque-1077 for density gradient centrifugation (400g for 45 minutes) as previously described.⁵⁴ The pellet is obtained from the last wash and resuspended in RPMI 1640 culture medium (2mM L-glutamine, 100 U/ml penicillin, 100 ug/ml streptomycin, 90 mg/dl glucose) at a final concentration of 5X10⁶ cells/ml. MNC isolated from the pre-CCT fasting blood sample will be cultured in medium supplemented with palmitate bound to fatty acid-free bovine albumin (4%) at varying concentrations spanning the physiological postabsorptive to pathophysiological range (0.4, 0.8, 1.2 and 2.0 mM), in the presence and absence of 1 ng/ml of lipopolysaccharide (LPS) endotoxin (Sigma, St Louis, MO). MNC isolated from the 120 minute CCT blood sample will be cultured without FFA supplementation in the presence and absence of 1 ng/ml of LPS. After a 24 hour incubation (5% CO₂ at 37°C), MNC supernatants will be collected and stored at -80°C until assayed.
- *Plasma Measurements:* All assays will be performed in the Reproductive Endocrine and Inflammation Laboratory except those for salicylate and progesterone which will be measured by the Clinical Chemistry Laboratory at IU Hospital. Glucose concentrations will be measured by the glucose oxidase method (YSI, Yellow Springs, OH) while plasma insulin concentrations will be measured by direct double antibody RIA (Linco Research, St. Charles, MO). C-peptide will be measured by a 2-site immunenzymatic sandwich assay (Roche Diagnostics, Indianapolis, IN). FFA will be measured by an enzymatic colorimetric assay (Wako Diagnostics, Mountain View, CA). TNF α , IL-6 and IL-1 β levels in plasma and in MNC culture supernatants will be measured by ELISA (Quantikine, R&D Systems, Minneapolis, MN). CRP levels will be measured by a high sensitivity ELISA (Alpha Diagnostics International, San Antonio, TX). Levels of LH, androstenedione, testosterone, DHEA-S, 17OH-progesterone and progesterone will be measured in duplicate by RIA (MP

Biomedicals LLC, Solon, OH). Sex Hormone Binding Globulin will be measured by electrochemiluminescence (Mayo Clinic, Rochester, MN). To reduce interassay variability, all samples from an individual subject will be measured in the same assay at the end of the study.

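### The progesterone cut-off for ovulation monitoring is in ng/dl in Table 1 and ng/ml in 6.1, a 100-fold conflict, and 6.6 leaves unclear which progesterone result decides

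*Combined protocol and SAP*

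**What the plan says.** **The cut-off.** The ovulation-monitoring row of Table 1 (section 6.0) schedules a progesterone measurement on the seventh day of the temperature rise and continues: "If P >2 ng/dl documented, vaginal sonography on day of & day after LH surge". The ovulation-monitoring paragraph of 6.1 describes the same sequence with a different unit: "The length of the cycle in which a luteal range progesterone (>2 ng/ml) is documented will be used to time initiation of midcycle urine" LH testing. It then adds: "Vaginal sonography will be performed in the CRC on the day of the color change signifying the LH surge and the following day".

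**The endpoint.** Section 12.2 describes the ovulation comparison in terms of luteal-range progesterone guided by the temperature charts and gives no number. Section 12.3 analyses ovulation by ultrasound evidence of follicular collapse, which 6.1 treats as definitive.

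**The assay.** The plasma-measurement paragraph of 6.6 places all assays in the research laboratory "except those for salicylate and progesterone which will be measured by the Clinical Chemistry Laboratory at IU Hospital". Later in the same paragraph, "17OH-progesterone and progesterone will be measured in duplicate by RIA". The paragraph closes by saying that, to limit between-assay variation, "all samples from an individual subject will be measured in the same assay at the end of the study".

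**The concern.** Table 1 and 6.1 govern the same step and cannot both be followed. Section 6.0 refers readers to Table 1 for an overview of the protocol, and ng/dl is a unit used elsewhere in this plan (for the testosterone AUC in 12.2), so nothing in the table warns that the unit may be a slip. Ovulation is part of the main objective and of the Aim 1 hypothesis in section 3.0. The progesterone value is the gate to the 12.3 endpoint and, under 12.2, is itself the endpoint.

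The assay text raises a second, smaller question. In 6.1 the progesterone result has to be known during the roughly 12 weeks of treatment, because the length of that cycle times the LH testing and the two scans. A result produced only at the end of the study cannot do this. If progesterone were measured both ways, no rule says which value is held against the cut-off.

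**Working it through.** **1. The plan's own figure.** The only design figure that uses this endpoint is the ovulation power in 12.2: 45 per arm, 10% ovulating on placebo, an increase of 40%, Fisher's exact test at 0.05, power over 80%. Exact enumeration, two-sided (sidedness is not stated), gives:

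| Placebo | Salsalate | Power |
|---|---|---|
| 10% | 50% (40 points higher) | 98.7% |
| 10% | 40% | 88.9% |
| 10% | 14% (a relative 40% increase) | 4.8% |

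The stated figure is reproduced if the increase is read as percentage points or as a rate of 40%. It does not depend on which progesterone unit is printed.

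**2. Unit conversion.** 1 dl = 100 ml, so 1 ng/ml = 100 ng/dl.

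- Table 1: 2 ng/dl = 2/100 = 0.02 ng/ml.
- Section 6.1: 2 ng/ml = 2 × 100 = 200 ng/dl.
- Ratio: 200/2 = 100.

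**3. Which results change class.**

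| Progesterone (ng/ml) | Table 1 | 6.1 |
|---|---|---|
| up to 0.02 | negative | negative |
| above 0.02, up to 2 | positive | negative |
| above 2 | positive | positive |

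Only the middle row is affected. The documents give no distribution of progesterone in these women, so the number of draws in that row cannot be calculated.

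**4. What a middle-row value would do.**

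- *Under 12.3:* it leads to LH monitoring and possibly two scans. It is not an ovulation unless follicular collapse is seen.
- *Under 12.2, scored in Table 1's unit:* it is counted as an ovulation.

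To show the sensitivity in that second case only, assume that a fraction f of non-ovulators in both arms is counted as positive, starting from 10% against 50%. The rates become 0.10 + 0.90f and 0.50 + 0.50f. At f = 0 the power is 98.7%. At f = 0.25 (32.5% against 62.5%) it is 75.2%, and at f = 0.5 (55% against 75%) it is 44.0%. The value of f is an assumption with no source in the documents.

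**5. The assay sentences set against 6.1.**

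- The exception for the hospital laboratory allows a result during treatment, which fits 6.1.
- The RIA sentence lists progesterone again and names no laboratory.
- The closing sentence covers all of a subject's samples and makes no exception for progesterone. Taken literally, it does not fit 6.1.

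**The case against.** The strongest reply is that the intended rule can be recovered. Section 6.1 is the operative procedure, it ties the luteal-range label to ng/ml, and 12.2 uses that same label, so the 12.2 endpoint follows 6.1 and not the table. Table 1 is an overview, and it is poorly preserved in the public text (its week columns stop at 8), so one misread character is possible. All of this stands. It makes a slip in the table the likely explanation, but no passage says so, and the unit should be checked in the source table.

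On the assay, the hospital-laboratory exception is explicit. The stated purpose of end-of-study assay suits the stored plasma from the HCG, cream and intravenous glucose tests, whereas 6.1 gives the 5 ml progesterone draw no storage instruction. Salicylate falls under the same exception, and section 11.0 has its levels sent to the DSMB as the study proceeds. This stands too, and makes the literal batch reading unlikely.

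Three stronger readings are tempting, and the documents do not support them:

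- *Every biphasic temperature chart becomes an ovulation.* Section 12.3 counts follicular collapse, so a low progesterone value alone is not an event there.
- *All temperature-triggered draws are affected.* Values above 2 ng/ml are positive under both cut-offs.
- *The ultrasound endpoint could not be collected.* This requires ignoring both the hospital-laboratory exception and the timing in 6.1.

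**Conclusion.** The conflict is real. The same decision threshold appears with two units that differ exactly 100-fold, and it controls entry to the ultrasound endpoint in 12.3 and gives luteal range its meaning for 12.2. The practical effect is confined to values above 0.02 and up to 2 ng/ml, and only if someone applies Table 1's unit. It would then be LH monitoring and scans that 6.1 does not call for, plus false ovulations if 12.2 were also scored that way. The size of that group is unknown, and the power values for f above are an illustration and not an estimate.

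The assay text is a genuine but lesser inconsistency: two assignments for one analyte, and a batching sentence that does not fit the need for a result during treatment.

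The conclusion assumes that the unit in Table 1 is printed as it reads in the public text. Neither correction alters a sample size or power figure. That 12.2 and 12.3 define ovulation differently is a separate matter, which correcting the unit does not resolve.

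**What to change.** - **Table 1 and 6.1:** reconcile them so that one cut-off in one unit applies. The luteal-range label supports the 6.1 unit, ng/ml; the investigator should confirm it. Repeat the number in 12.2 so that the endpoint does not depend on a cross-reference.
- **Section 6.6:** state that the contemporaneous clinical-laboratory progesterone result decides the endpoint and is exempt from end-of-study batching. Remove progesterone from the RIA list, or label that RIA as descriptive. Since 6.6 and 11.0 also name different laboratories for salicylate, correct that in the same edit.
- **Timing:** settle this before unblinding. If monitoring has already started, record which cut-off was used.

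The cost is wording in Table 1, 6.6 and 12.2. No new samples, visits or assays are needed.
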